9.5.1.4.3 Dose Modifications

Common toxicities including myelosuppression, nausea, gastrointestinal toxicity, fatigue, pyrexia, headache, weight decrease, dyspnea, rash, and stomatitis should be managed according to institutional standards or accepted guidelines (eg, American Society of Clinical Oncology [ASCO] guidelines for the use of WBC growth factors [26]). Growth factor support may be administered as needed according to institutional standard of care.

Vadastuximab Talirine

[Table 2](#) describes guidelines for dose modifications of vadastuximab talirine (Phase 1 Portion) or blinded study treatment (Phase 2 Portion) for toxicity.

Dose delays of any study treatment are permitted. If dosing is delayed for azacitidine, vadastuximab talirine (Phase 1 Portion), or blinded study treatment (Phase 2 Portion), both study treatments should be held and resumed together on the same schedule except when one agent is omitted during a cycle due to toxicity.

For patients who achieve a response to therapy, dose decreases, delays, or dose re-escalation (to original dose level) are permitted at the discretion of the medical monitor and site Investigator. Following achievement of marrow blast clearance to $<5\%$ (ie, a CR or marrow CR), patients originally treated with a dose higher than 5 mcg/kg of study drug will receive azacitidine with vadastuximab talirine (Phase 1 Portion) or blinded study treatment (Phase 2 Portion) as continuation therapy at the maintenance dose of 5 mcg/kg in subsequent cycles.

Azacitidine, vadastuximab talirine (Phase 1 Portion), or blinded study drug (Phase 2 Portion) may be permanently discontinued in the event of unacceptable related toxicity. Subjects will not be considered off study treatment until both study treatments are discontinued.

If subjects become candidates for stem cell transplant after enrollment, vadastuximab talirine must be discontinued at least 30 days prior to initiation of preparative regimen for stem cell transplant.

Table 2: Dose Modifications for Vadastuximab Talirine-Associated Toxicity

Category	Event	Action

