Hematologic toxicity with marrow blast count <5% ^a	≥ Grade 3 neutropenia or thrombocytopenia	Cycles of treatment may be delayed up to 14 days ^b until hematologic recovery is observed. Adequate hematologic recovery is defined as neutropenia and thrombocytopenia improved to < grade 3 (unsupported), OR ANC / platelets ≥ [(NADIR COUNT ^c) + (BASELINE COUNT ^d – NADIR COUNT) x 0.50] If hematologic recovery as defined above has not occurred within 14 days of the end of the cycle (by Day 42), omit vadastuximab talirine (Phase 1) or blinded study treatment (Phase 2) from the next cycle, and initiate next dose of azacitidine based on marrow cellularity as defined in Table 3.
Hematologic toxicity with marrow blasts ≥5% ^b	≥ Grade 3 neutropenia or thrombocytopenia	Treatment may continue without dose modification.
Clinically significant non-hematologic toxicity or asymptomatic non-hematologic laboratory abnormality (with the exception of hepatic toxicity)	≥ Grade 3 event	Treatment delay of up to 14 days is permitted until resolution of toxicity to < grade 3.
Laboratory evidence of hepatic toxicity (elevation in ALT, AST, or total bilirubin)	≥ Grade 3 event	Treatment delay of up to 14 days is required until resolution of toxicity to ≤ grade 1 or baseline. If toxicity has not resolved within 14 days, permanently discontinue vadastuximab talirine (Phase 1) or blinded study treatment (Phase 2)

ALT = alanine aminotransferase; ANC = absolute neutrophil count; AST = aspartate aminotransferase.

- a If cytopenias above grade 3 (e.g., ANC <1000/mm³ or platelets <50 x 10⁹/L) are present at Day 28 of a cycle in which no response assessment is required, an ‘unscheduled’ bone marrow biopsy is required within 14 days of the scheduled end of the cycle (eg, between Day 28 and Day 42). If the bone marrow cellularity is ≤10%, vadastuximab talirine or blinded study treatment will be permanently discontinued. If marrow cellularity is >10%, follow guidance as above.
- b Delays of >14 days may be permitted with approval of the medical monitor.
- c Nadir Count = the lowest count reached during the treatment cycle.
- d Baseline Count = counts prior to Cycle 1 of study treatment.

Azacitidine

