## 5.0 Definitions

**Absolute Dose Intensity (ADI):** is defined as the actual dose ( $\mu\text{g}/\text{kg}$ ) per unit of time that the subject received over the entire treatment period. Actual time for the denominator will be calculated separately for vadastuximab talirine and azacitidine as follows:

Vadastuximab talirine: last day 1 dose date of azacitidine where vadastuximab talirine was received in that cycle +28 - first dose of any study drug

Azacitidine: last day 1 dose date of azacitidine +28 - first dose of any study drug

**AEs Leading to Discontinuation of Study Drugs:** are those indicated by “Reason for discontinuing treatment” of AE (linked by AE number) on the End of Treatment Summary page of the CRF.

**Age (years):** will be calculated with the SAS INTCK function using informed consent date and birth date.

**ATA Incidence Rate:** is defined as the proportion of patients that develop ATA at any time during the study.

**Baseline:** is defined as the most recent measurement prior to the first dose of any study treatment unless otherwise defined in a specific section of the SAP.

**Complete Response:** is defined as an answer of “Complete Remission” for the question “Response Assessment” in CRF form of “Response Assessment”.

**Concomitant Medication:** is defined as any medication ongoing at the start of vadastuximab talirine or Placebo dosing or with a start date on or after the first dose date of any study treatment dose date up to 30 days post last dose or EOT whichever is longer. Medications with start and end dates before the first dose date of any study treatment may be concomitant if the medication is marked as ongoing. For medications with missing or partial start dates, a missing start date will be imputed with the first dose date of any study treatment, missing month and day for a partial start date will be imputed with January 1st, and missing day for a partial start date will be imputed with the first day of the month.

**Days:** The following unit conversion will be implemented unless otherwise specified:

$$\text{Months} = \text{Days} / 30.4375$$

$$\text{Years} = \text{Days} / 365.25.$$

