#### 9.6.1.2 Adverse Events and Serious Adverse Events

AEs will be summarized by descending frequency of MedDRA PT unless otherwise specified. For incidence reporting, if a subject reports more than one AE that was coded to the same SOC or PT, the subject will be counted only once for that specific SOC or PT. See [Section 5](#) for definition of pre-existing AEs, TEAEs, related AEs, SAEs, infusion-related reaction AEs and AEs leading to vadastuximab talirine treatment discontinuation. All the AEs summarized in tables are TEAEs, except related AEs or unless otherwise indicated. All AEs will be coded by SOC, MedDRA PT, and severity grade using NCI CTCAE. All recorded AEs will be included in the data listings.

A summary table of number and percent of the following AE categories will be provided by treatment or dose level and total as follows:

- Pre-existing AEs
- All TEAEs
- TEAEs related to vadastuximab talirine or placebo
- TEAEs related to azacitidine treatment
- TEAEs with outcome of death
- Treatment-emergent SAEs
- Treatment-emergent SAEs related to vadastuximab talirine or placebo
- Treatment-emergent SAEs related to azacitidine treatment

- TEAEs leading to dose delay of vadastuximab talirine or placebo treatment
- TEAEs leading to dose delay of azacitidine treatment
- TEAEs leading to dose interruption (full dose received) of vadastuximab talirine or placebo treatment
- TEAEs leading to dose interruption (full dose received) of azacitidine treatment
- TEAEs leading to dose being stopped early (full dose not received) of vadastuximab talirine or placebo treatment
- TEAEs leading to dose being stopped early (full dose not received) of azacitidine treatment
- TEAEs leading to dose reduction of vadastuximab talirine or placebo treatment
- TEAEs leading to dose reduction of azacitidine treatment
- TEAEs leading to treatment discontinuation
- Treatment-emergent SAEs leading to treatment discontinuation
- Vadastuximab Talirine -related TEAEs leading to treatment discontinuation
- Azacitidine -related TEAEs leading to treatment discontinuation
- Grade 3-5 TEAEs
- Grade 3-5 vadastuximab talirine or placebo treatment-related TEAEs
- Grade 3-5 azacitidine treatment-related TEAEs
- Infusion-related reaction TEAEs

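### AEs leading to discontinuation are read only from the End of Treatment page, so an AE that ends vadastuximab or blinded drug can be missed when azacitidine continues

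*SAP*

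**What the plan says.** - **Source of the variable.** SAP 5.0 defines AEs leading to discontinuation of study drugs as those giving a reason "of AE (linked by AE number) on the End of Treatment Summary page of the CRF". It names no other source.
- **Stopping one agent.** Protocol 9.5.1.4.3 says azacitidine, vadastuximab talirine or blinded drug "may be permanently discontinued in the event of unacceptable related toxicity". Table 2 goes further in two situations. For hepatic laboratory toxicity of grade 3 or higher that has not resolved in 14 days, it requires permanent stopping of vadastuximab or blinded drug and names no other agent. For a low-cellularity marrow it says: "If the bone marrow cellularity is ≤10%, vadastuximab talirine or blinded study treatment will be permanently discontinued".
- **When treatment ends.** The same section states: "Subjects will not be considered off study treatment until both study treatments are discontinued".
- **What the tables are meant to show.** SAP 9.6.1.2 sends the reader to Section 5 for the definition of "AEs leading to vadastuximab talirine treatment discontinuation". Its list of AE categories splits delay, interruption, early stopping of a dose and reduction by agent. It does not split permanent discontinuation by the agent stopped.
- **Protocol commitment.** Protocol 13.6.7 promises both a summary and a listing of AEs that led to treatment discontinuation.

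**The concern.** In an add-on design, a basic tolerability question is how many subjects had to give up the added drug because of toxicity. Here the added drug can be withdrawn permanently while the background drug goes on, perhaps for many cycles. A variable built on the reason for ending all treatment answers a different question.

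Safety of the combination is a secondary objective in both portions (Protocol 8.2), and hepatobiliary serious AEs are events of special interest (Protocol 12.1.4). An unresolved hepatic toxicity that ends vadastuximab is therefore an event the discontinuation table should show, and it is one that the stated derivation can lose.

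**Working it through.** No sample size, power or event count enters this point, and the plan gives no figure to reproduce. The check traces one subject through the rules.

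1. Blinded drug is stopped permanently for toxicity under Protocol 9.5.1.4.3. For a hepatic withdrawal, Protocol 12.1.1 makes the laboratory abnormality recordable as an AE because it led to discontinuation, so an AE record should exist.
2. Table 2 does not stop azacitidine. Its dosing is left to the treating physician, and Table 3 schedules further azacitidine cycles even in the lowest marrow-cellularity column. Continuing azacitidine is therefore an expected path, though not a required one.
3. While azacitidine continues, the subject is still on study treatment, so no end-of-treatment reason is due.
4. The table entry then depends on what happens to azacitidine, assuming one End of Treatment page per subject:

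| After the AE that ended vadastuximab or blinded drug | Result under SAP 5.0 |
|---|---|
| Azacitidine stops at the same time for the same AE | Counted correctly |
| Azacitidine stops later, same AE linked | Counted |
| Azacitidine stops later for a different AE | Subject counted, but under the other AE; the related and serious rows may also be wrong |
| Azacitidine stops later for progression or another non-AE reason | Not counted |
| Azacitidine still ongoing at the analysis | Not counted |

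The same gap exists in mirror image if azacitidine alone is stopped for toxicity.

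5. Could another planned row catch the event? The early-stop rows concern a dose not given in full. The delay and reduction rows concern doses still to be given. The vadastuximab-related and azacitidine-related discontinuation rows divide events by attributed cause, not by which agent was stopped. None records permanent withdrawal of one agent.
6. Is the omission intended? SAP 9.6.1.2 describes the Section 5 definition as covering vadastuximab discontinuation, and SAP 5.0 defines study drug as vadastuximab alone. Elsewhere the SAP keeps the agents apart: dose-intensity denominators are agent-specific (5.0), and deaths are classified by time from the last vadastuximab dose (9.6.1.3). The discontinuation rule is out of line with both.

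Scale only, not an estimate: with 106 subjects randomised 1:1, an arm has 106/2 = 53, so each missed subject lowers that arm's rate by 1/53 = 1.9 percentage points. In a Phase 1 cohort of six it is 1/6 = 16.7 points. The number missed could be zero.

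**The case against.** The strongest reply is that the CRF dated 29 August 2017 is not among the documents. The SAP heading refers to study drugs in the plural, dosing is recorded on separate pages for each agent, and 9.6.1.2 reads the definition as being about vadastuximab. The End of Treatment page might therefore hold a reason per agent, and nothing would be lost. That possibility stands and makes the finding conditional. It does not remove the problem, because the SAP cites a single treatment-discontinuation reason and states no per-agent rule. Protocol 10.3 times the visit from the last dose of either or both agents, but that loose wording does not override the both-agents rule.

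A reader might also infer that the rule drops all the withdrawals mandated by Table 2 and makes vadastuximab look better tolerated. The documents do not support that. An event is lost only if azacitidine continues and the final reason is not that AE; the physician may stop both agents together. Table 2 applies to blinded drug in both arms, and cytopenias are also part of the disease, so the direction between arms is not established.

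Much of the information also survives elsewhere: general and grade 3–5 AE tables, serious AEs, laboratory shift tables, and exposure summaries with adjustment reasons. The DLT tabulation and ORR do not use this definition.

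Finally, the AE items listed in Protocol 12.1.2 include no action-taken field, so a fix cannot assume one. SAP 1.1 already reports that hematologic improvement could not be derived because the data were not captured.

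**Conclusion.** The concern holds in conditional form. As written, SAP 5.0 can yield an incomplete discontinuation summary and listing, and it does not deliver what SAP 9.6.1.2 cites it for. This rests on three conditions: the End of Treatment page records one overall reason, azacitidine continues after vadastuximab or blinded drug is stopped for toxicity, and the final reason is not that AE. The first cannot be checked without the CRF.

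The size of the undercount cannot be estimated, since no rate of single-agent discontinuation is given. A heavier undercount in the experimental arm follows only if vadastuximab causes more such toxicity than placebo. The effect is confined to the discontinuation rows and their listing. It should be corrected before database lock; it does not touch the primary analysis.

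**What to change.** In SAP 5.0, define AEs leading to permanent discontinuation separately for:

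- (a) vadastuximab or blinded drug, whether or not azacitidine continues;
- (b) azacitidine, whether or not the other agent continues;
- (c) all study treatment.

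Take (a) and (b) from the agent-specific Treatment CRF pages and the dose-adjustment reasons that SAP 9.3.1 already summarises. Keep the End of Treatment page for (c). State in the SAP whether that page is completed once or per agent.

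Where no AE link is recorded, identify subjects whose last vadastuximab or blinded dose precedes continued azacitidine, and assign the reason from recorded data. In Phase 2 do this by blinded review before unblinding. Protocol 13.6.4 unblinds for ORR while some subjects may still be on treatment, so the assignment rule must be fixed beforehand and applied unchanged to later stops.

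In SAP 9.6.1.2, replace the discontinuation row with rows (a), (b) and (c), and do the same for the serious, vadastuximab-related and azacitidine-related versions: 4 rows become 4 × 3 = 12. Extend the listing to match.

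The cost is SAP wording, some programming and a review of unlinked cases. The agent-specific treatment pages and agent-specific dose-action rows already exist, so no new visit or procedure is needed, but any case with no recorded reason should be shown as such. The reported discontinuation rate may become less favourable. No stopping rule changes.

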
STUDY DESIGN AND METHODOLOGY: This is a phase 1/2 study to evaluate the combination of vadastuximab talirine and azacitidine in subjects with previously untreated IPSS Intermediate-2 or High risk MDS. In the Phase 1 Portion of the trial, escalating doses of vadastuximab talirine will be evaluated in combination with azacitidine, and 1 dose will be selected for the randomized, double-blind, placebo-controlled Phase 2 Portion of the study, which is designed to compare the ORR between 2 study arms.
 
Phase 1 Portion – Open-Label Dose Evaluation
 
Cohorts of 6 dose-limiting toxicity (DLT)-evaluable subjects will be enrolled in an open-label fashion to receive vadastuximab talirine (intravenous [IV] push in combination with azacitidine (75 mg/m²; subcutaneously [SC] or IV) in 28-day cycles, starting at 5 mcg/kg vadastuximab talirine. The DLT-evaluable population will include all Phase 1 subjects who have completed at least Cycle 1 of treatment
		

(Cycle 1 of treatment is completed when the patient receives the first dose of azacitidine on Day 1 of Cycle 2) or discontinued study treatment because of adverse events (AEs), or for a safety-related reason before having had the opportunity to receive the first dose of azacitidine on Day 1 of Cycle 2. In the Phase 1 Portion of the study, DLTs will be defined as posttreatment grade 4 neutropenia or grade 4 thrombocytopenia lasting >42 days from the start of therapy, in the absence of evidence of active MDS, or any grade 3 or higher non-hematologic toxicity that is clearly NOT resulting from underlying MDS or azacitidine, with the exception of:

- a. Grade 3 allergic reaction, fatigue, asthenia, anorexia, or constipation
- b. Grade 3 nausea, vomiting, or diarrhea not requiring tube feeding or total parenteral nutrition or hospitalization
- c. Febrile neutropenia (which resolves with appropriate treatment or marrow recovery), infection, bleeding, or other expected direct complications of cytopenias due to active MDS

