9.1.1 Phase 1 Portion – Open-Label Dose Evaluation

Cohorts of 6 dose-limiting toxicity (DLT)-evaluable subjects will be enrolled in an open-label fashion to receive vadastuximab talirine in combination with azacitidine in 28-day cycles, starting at 5 mcg/kg vadastuximab talirine. The DLT-evaluable population will include all Phase 1 subjects who have completed at least Cycle 1 of treatment (Cycle 1 of treatment is completed when the patient receives the first dose of azacitidine on Day 1 of Cycle 2) *or* discontinued study treatment because of AEs, or for a safety-related reason before having had the opportunity to receive the first dose of azacitidine on Day 1 of Cycle 2. In the Phase 1 Portion of the study, DLTs will be defined as posttreatment grade 4 neutropenia or grade 4 thrombocytopenia lasting >42 days from the start of therapy, in the absence of evidence of active MDS, or any grade 3 or higher non-hematologic toxicity that is clearly NOT resulting from underlying MDS or azacitidine, with the exception of:

- a. Grade 3 allergic reaction, fatigue, asthenia, anorexia, or constipation
- b. Grade 3 nausea, vomiting, or diarrhea not requiring tube feeding or total parenteral nutrition or hospitalization
- c. Febrile neutropenia (which resolves with appropriate treatment or marrow recovery), infection, bleeding, or other expected direct complications of cytopenias due to active MDS

If 2 or more subjects in a 6-subject cohort have DLTs, that dose level will be considered to have exceeded the MTD. If 5 mcg/kg vadastuximab talirine in combination with azacitidine is considered tolerable (≤ 1 of 6 subjects experiences a DLT), a cohort of 6 DLT-evaluable subjects will receive 10 mcg/kg vadastuximab talirine and azacitidine. If 10 mcg/kg vadastuximab talirine in combination with azacitidine is considered tolerable, a cohort of 6 DLT-evaluable subjects will receive 15 mcg/kg, and if 15 mcg/kg vadastuximab talirine in combination with azacitidine is considered tolerable, a cohort of 6 DLT-evaluable subjects will receive 20 mcg/kg. If 5 mcg/kg vadastuximab talirine in combination with azacitidine is not considered tolerable (> 1 of 6 subjects experiences a DLT), a cohort of 6 DLT-evaluable subjects will receive 3 mcg/kg vadastuximab talirine and azacitidine. The dose-escalation plan is presented in [Figure 1](#).

Figure 1: Study Schematic – Phase 1 Portion

DLT = dose-limiting toxicity; MTD = maximum tolerated dose.

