13.5.3 DLT-Evaluable Population

The DLT-evaluable population will include all Phase 1 subjects who have completed at least Cycle 1 of treatment (Cycle 1 of treatment is completed when the patient receives the first dose of azacitidine on Day 1 of Cycle 2) *or* discontinued study treatment because of AEs or for a safety-related reason before having had the opportunity to receive the first dose of azacitidine on Day 1 of Cycle 2. Subjects in the DLT-evaluable population will be grouped by assigned dose level.

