#### 3.1.1 Phase 1 Portion – Open-Label Dose Evaluation

Cohorts of 6 dose-limiting toxicity (DLT)-evaluable subjects will be enrolled in an open-label fashion to receive vadastuximab talirine in combination with azacitidine in 28-day cycles, starting at 5 mcg/kg vadastuximab talirine. DLT-evaluable population will include all Phase 1 subjects who have completed at least Cycle 1 of treatment (Cycle 1 of treatment is completed when the patient receives the first dose of azacitidine on Day 1 of Cycle 2) or discontinued study treatment because of adverse events (AEs) or for a safety-related reason before having had the opportunity to receive the first dose of azacitidine on Day 1 of Cycle 2. In the phase 1 Portion of the study, DLTs will be defined as posttreatment grade 4 neutropenia or grade 4 thrombocytopenia lasting >42 days from the start of therapy, in the absence of evidence of active MDS, or any grade 3 or higher non-hematologic toxicity that is clearly NOT resulting from underlying MDS or azacitidine, with the exception of:

[figure not shown]
- a. Grade 3 allergic reaction, fatigue, asthenia, anorexia, or constipation
- b. Grade 3 nausea, vomiting, or diarrhea not requiring tube feeding or total parenteral nutrition or hospitalization,
- c. Febrile neutropenia (which resolves with appropriate treatment or marrow recovery), infection, bleeding, or other expected direct complications of cytopenias due to active MDS.

If 2 or more subjects in a 6-subject cohort have DLTs, that dose level will be considered to have exceeded the maximum tolerated dose (MTD). If 5 mcg/kg vadastuximab talirine in combination with azacitidine is considered tolerable ( $\leq 1$  of 6 subjects experiences a DLT), a cohort of 6 DLT-evaluable subjects will receive 10 mcg/kg vadastuximab talirine and azacitidine. If 10 mcg/kg

vadastuximab talirine in combination with azacitidine is considered tolerable, a cohort of 6 DLT-evaluable subjects will receive 15 mcg/kg, and if 15 mcg/kg vadastuximab talirine in combination with azacitidine is considered tolerable, a cohort of 6 DLT-evaluable subjects will receive 20 mcg/kg. If 5 mcg/kg vadastuximab talirine in combination with azacitidine is not considered tolerable (>1 of 6 subjects experiences a DLT), a cohort of 6 DLT-evaluable subjects will receive 3 mcg/kg vadastuximab talirine and azacitidine. The dose escalation plan is presented in Figure 1.

Figure 1: Study Schematic – Phase 1 Portion

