**Deaths:** Subject deaths will be determined from End of Study CRF page (where reason for discontinuation is death) and from AE CRF page (where CTCAE grade is 5 or outcome is “fatal”) and from the follow-up CRF page (where the answer to the question “Is the patient alive?” is “No”). The number of days between vadastuximab talirine or placebo last dose and death will be calculated as (date of death – last vadastuximab talirine or placebo dose date + 1).

**Dose-Limiting Toxicity:** see [Section 3.1.1](#).

**DLT Evaluable Subject:** is defined as all Phase 1 subjects who have completed at least Cycle 1 of treatment (Cycle 1 of treatment is completed when the patient receives the first dose of azacitidine on Day 1 of Cycle 2), or discontinued study treatment because of AEs or for a safety-related reason (defined as AE, Investigator Decision, or Progressive Disease) before having had

the opportunity to receive the first dose of azacitidine on Day 1 of Cycle 2, or who experienced a DLT.

**Duration of Response:** is defined as the time from first observation of response (PR+CR/Marrow CR) to disease progression/relapse or death from any cause, whichever occurs first.

**Duration of Treatment:** is defined as time from the first dose of any study drug until 28 days after the last day 1 dose date, or until : last contact date if the patient is still on treatment at the time of the analysis.

Minimum(Last day 1 dose date + 27, death date, last contact date) – first dose date +1

**Infusion Related Reactions AE:** is defined for those AEs that have responses of “Yes” for the question “Were there any infusion-related reactions?” in the CRF forms “Treatment – Blinded Study Drug”, “Treatment – Azacitidine”, or “Treatment – Vadastuximab Talirine”.

**Hematologic Improvement:** is defined in [Table 1](#)

**Hematologic Improvement (HI) Rate:** is defined in as the proportion of subjects with Erythroid response, Platelet response or Neutrophil response as defined in [Table 1](#).

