### 6.3 DLT-Evaluable Set

The DLT-evaluable set will include all phase 1 subjects who completed at least Cycle 1 of treatment (Cycle 1 of treatment is completed when the patient receives the first dose of azacitidine on Day 1 of Cycle 2) or discontinued study treatment because of AEs or for a safety-related reason before having had the opportunity to receive the first dose of azacitidine on Day 1 of Cycle 2, or who had a DLT. Subjects in the DLT-evaluable set will be grouped by actual dose level.

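### SAP 5.0 widens the DLT-evaluable set to Progressive Disease and any Investigator Decision without declaring it, and no definition requires the Cycle 1 vadastuximab talirine dose

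*SAP*

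**What the plan says.** **Protocol.** Section 13.5.3 counts as evaluable those who completed Cycle 1, meaning that they received the first azacitidine dose of Cycle 2, and those who "discontinued study treatment because of AEs or for a safety-related reason before having had the opportunity to receive the first dose of azacitidine". The synopsis and 9.1.1 say the same, and none of the three says what a safety-related reason is. Grouping in 13.5.3 is by assignment: "Subjects in the DLT-evaluable population will be grouped by assigned dose level". Section 9.4.3.1 lists progressive disease, AE and investigator decision as separate reasons for stopping study drug.

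**SAP.** Four places bear on the same set:
- 3.1.1 repeats the protocol: "discontinued study treatment because of adverse events (AEs) or for a safety-related reason before having had the opportunity". It has no list of reasons and no DLT clause.
- 5.0 gives the list, "for a safety-related reason (defined as AE, Investigator Decision, or Progressive Disease", and adds a further route at the end: "the opportunity to receive the first dose of azacitidine on Day 1 of Cycle 2, or who experienced a DLT".
- 6.3 has the DLT clause but not the list, and changes the grouping: "or who had a DLT. Subjects in the DLT-evaluable set will be grouped by actual dose level". For Phase 1, SAP 5.0 takes the actual arm from the vadastuximab talirine dose received in Cycle 1.
- 7.1 (Safety Monitoring Committee) ends the DLT period early only when treatment stops for toxicity related to study treatment.

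SAP 1.1, on changes from the protocol, mentions only disposition by cycle and hematologic improvement. SAP 9.6.1.1 reports the number and percentage with a DLT by dose level on this set.

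**The concern.** A DLT percentage should rest on subjects who either had a DLT or were watched long enough, on the drug, to have had one. Someone who leaves in Cycle 1 for progression or for a non-safety decision by the investigator meets neither condition. Progression fits especially badly: the DLT definition in protocol 9.1.1 sets aside toxicity that results from the underlying MDS, and its hematologic limb needs absence of active MDS, which a progressing subject can hardly satisfy.

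Exposure is a related gap. Vadastuximab talirine is given on the last azacitidine day (Day 7 or Day 9), yet every definition judges completion by azacitidine alone.

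At stake is the clarity of the main Phase 1 safety table. Its denominator can differ by SAP section, and a reader of the report would not be told that it differs from the protocol.

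**Working it through.** **1. The plan's own figures.** Protocol 13.2 and SAP 3.2 give the chance of calling a dose tolerable (at most 1 DLT in 6).
- True rate 10%: 0.9^6 + 6 × 0.1 × 0.9^5 = 0.5314 + 0.3543 = 0.8857, stated as 88.6%.
- True rate 50%: 7 × 0.5^6 = 0.1094, stated as 10.9%.

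Both reproduce. They treat all six subjects as fully at risk of a DLT.

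**2. Who enters by which route.** These are subjects who leave before the first Cycle 2 azacitidine dose.

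| Early leaver | Protocol 13.5.3, SAP 3.1.1 | SAP 5.0 | SAP 6.3 |
|---|---|---|---|
| AE | in | in | in |
| Investigator Decision, for safety | arguably in | in | arguably in |
| Investigator Decision, not for safety; no DLT | out on a plain reading | in | depends on whether the 5.0 list is applied |
| Progressive Disease, no DLT | out on a plain reading | in | depends on whether the 5.0 list is applied |
| DLT, left for another reason (e.g. subject decision) | out on a plain reading | in | in |

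**3. Effect of the widened routes.** Anyone with a DLT is already in through the DLT clause. So b subjects who enter only by Progressive Disease or a non-safety Investigator Decision have no DLT, and D/N becomes D/(N + b). With N = 6 others:

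| DLTs | b = 0 | b = 1 | b = 2 |
|---|---|---|---|
| 0 | 0.0% | 0.0% | 0.0% |
| 1 | 16.7% | 14.3% | 12.5% |
| 2 | 33.3% | 28.6% | 25.0% |

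**4. Effect of the DLT clause.** If a subjects enter only through that clause, they add to both parts, and the SAP figure is (D + a)/(N + a + b). This falls below D/N only if b × D > a × (N − D). With D = 1 and N = 6:
- a = 0, b = 1: 1/7 = 14.3%, below 16.7%.
- a = 1, b = 0: 2/7 = 28.6%, above.
- a = 1, b = 1: 2/8 = 25.0%, above.

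The net shift against the protocol therefore has no fixed sign. The documents give no rate of early exit, so a and b cannot be estimated.

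**5. The never-dosed subject.** Take someone without a DLT who is otherwise evaluable but received no vadastuximab talirine in Cycle 1. Protocol 13.5.3 counts that subject at the assigned dose. SAP 6.3 also has the subject in the set, but the actual-arm definition supplies no dose level, so the subject has no column in the 9.6.1.1 table.

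**The case against.** The strongest reply is that the SAP only makes an undefined term programmable. The protocol has two limbs, AEs and safety-related reasons. The second adds nothing unless it reaches stops not coded as AE, and protocol 13.3 expects the SAP to expand on the protocol. This stands for Investigator Decisions taken for safety, so a reader should not treat that whole category as a departure. It does not carry Progressive Disease or unqualified Investigator Decisions: protocol 9.4.3.1 keeps both apart from AE, and SAP 7.1 recognizes only treatment-related toxicity as an early end to the DLT period.

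Other points stand in part.
- SAP 5.0 is the definitions section and agrees with 6.3 on the DLT clause, so most programmers would probably apply 5.0. The mismatch with 3.1.1 is then largely editorial.
- The progression route is narrow, since the first scheduled response assessment is Day 22-29 of Cycle 2. It is not closed: protocol 10.2.1.1 has a Cycle 1 Day 28 marrow biopsy for some Phase 1 subjects. Investigator Decision has no such limit.
- Phase 1 is descriptive (SAP 9.0). SAP 9.1 lists discontinuation reasons, last-dose dates and analysis sets, so a careful reader could recompute the percentages.
- Removing the leavers has its own bias. Early leavers would then count only when they have a DLT, which pushes the proportion modestly upward.

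**Conclusion.** The point holds and is minor. SAP 5.0 counts some subjects with incomplete DLT observation as evaluable without a DLT, and SAP 1.1 does not declare it. Each such subject lowers the percentage for that dose: 2.4 points for one leaver and one DLT among six others (16.7% to 14.3%), 4.2 points for two (16.7% to 12.5%). There is no effect without a DLT or without such a leaver. These are illustrations that assume the leavers come on top of six other evaluable subjects.

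Three stronger readings are not supported.
- That the SAP as a whole understates the DLT rate relative to the protocol: the DLT clause acts the other way.
- That the stated 10.9% chance of calling a dose with a 50% DLT rate tolerable is wrong, or that escalation is weakened: the rule counts DLTs, and the documents do not show that cohorts are filled with the SAP 5.0 definition.
- That never-dosed subjects dilute the SAP's dose-level percentages: under the actual-dose grouping they have no dose level. The dilution would arise under the protocol's assigned grouping.

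**What to change.** 1. In SAP 5.0, remove Progressive Disease from the list and limit Investigator Decision to documented safety reasons. Keep subjects who stop for an AE and anyone with a DLT.
2. Require that a subject counted as evaluable without a DLT received the Cycle 1 vadastuximab talirine dose.
3. Add a sensitivity line to the DLT table that includes dosed subjects who left by Progressive Disease or Investigator Decision. It shows how far the upward bias of the main proportion could matter.
4. Use one dose grouping, assigned or actual, and say where a subject with a DLT but no vadastuximab talirine dose is shown. Reconcile SAP 3.1.1, 5.0, 6.3 and 7.1 with protocol 9.1.1 and 13.5.3, and declare every departure, including the DLT clause, in SAP 1.1.

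The cost is SAP wording and one table line. Aligning the protocol text needs an amendment under protocol 16.2 and can wait for the next one, which should also state which definition is used to fill cohorts. The downside is the modest upward bias in the main proportion, which the sensitivity line makes visible.
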